We performed a 40-patient double-blind pilot RCT examining the impact of 1 gram of CaCl₂ or saline placebo in addition to standard oxytocin during cesarean delivery in parturients with heightened risk of uterine atony. In the pilot study, we demonstrated feasibility by successfully enrolling all 40 patients in a one-year timeframe despite a lack of dedicated funding or research staff. The drug infusion was well-tolerated, with no adverse hemodynamic consequences. An equal number of patients in the calcium and placebo groups reported possible drug side effects including flushing, nausea, or vomiting (30% in each arm). Obtaining and measuring venous blood specimens for PK analysis also proved feasible.

Although inferring intervention efficacy is not the aim of a pilot trial, there were several trends noted within our pilot trial data that suggest CaCl₂ warrants a larger, definitive study as a potential intervention for uterine atony (**Table 1**). Only 20% of patients who received calcium had uterine atony, pre-defined as requirement for a second line uterotonic agent, placement of an intrauterine balloon for tamponade, or hemorrhage with blood loss >1000mL, compared to 50% of patients who received the saline placebo infusion (relative risk 0.38, *P*=0.07, 95% CI 0.15-1.07, NNT 3.3). Blood loss, uterine tone score, total oxytocin dose, and intraoperative fluid requirements all showed similar promising trends (**Table 1**).

Table 1: Outcomes related to atony and hemorrhage, pilot RCT. Values are provided as median [interquartile range]

	Calcium (n=20)	Placebo (n=20)	P value
Uterine atony incidence	20% (n=4)	50% (n=10)	0.07
Blood Loss (mL)	750 [600-800]	850 [650-1000]	0.15
Uterine tone NRS (0-10)	9 [8-9]	8 [7-9]	0.13
Oxytocin			
Total bolus dose (units)	2 [2-2]	2 [2-4]	0.14
Maximal infusion rate (units/hr)	7.5 [7.5-15]	15 [7.5-22.5]	0.41
Fluids and transfusion			
Crystallloid (mL)	1200 [1000-2000]	1750 [1500-2000]	0.03
Colloid (mL)	0 [0-0] range [0-500]	0 [0-0] range [0-1000]	0.08

[figure not shown]

Figure 1: pilot data: ionized calcium concentrations over time. Blue data points represent ionized calcium venous blood concentrations from 13 patients who received calcium, and red data points represent ionized calcium in 11 patients who received a saline placebo infusion.

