Inter-subject random effects (e.g., subject to subject differences) on model parameters will be estimated and applied using additive, proportional, and exponential models as appropriate. Residual intrasubject variability (e.g., noise) will typically require an additive and multiplicative error model. The influence of covariates effects (e.g., age, weight, gestational age, pH, uterotronics including oxytocin, methylergonovine, and carboprost) on model parameters will be analyzed by serial inclusion/exclusion with significance determined by the likelihood ratio test. Covariates on the PK and PD parameters deemed significant by likelihood ratio test will be validated using jackknife cross-validation as described by Sheiner¹⁷ and only included in the final model if validated.

N	Parameter	Mean	95% Confidence Bound		Range	Correction	Corrected Range
			Lower	Upper			
24	Cl_1	0.93	0.78	1.70	98%		173%
	V_1	75.6	52.8	88.6	47%	1.76	83%
	Baseline	1.18	1.16	1.19	3%		4%
60	Cl_1	0.93	0.80	1.43	68%		94%
	V_1	75.6	62.9	84.0	28%	1.39	39%
	Baseline	1.18	1.17	1.19	2%		2%
120	Cl_1	0.93	0.81	1.24	46%		57%
	V_1	75.6	68.5	80.6	16%	1.26	20%
	Baseline	1.18	1.17	1.18	1%		1%

Table 2: Bootstrap analysis using pilot ionized calcium values. The mean and 95% confidence intervals are shown for each parameter.

[figure not shown]

Figure 2: Ordinal model of uterine NRS showing hypothetical probability of $NRS > 3$, > 6 , and > 8 as a function of calcium

Table 2 shows the results of 1000 bootstrap replications of data from the original 24 individuals in the pilot PK study, resampled with N=60 (half of the proposed study population), and N=120 (the entire proposed study population)¹⁸. As expected, the estimates are more precise with increasing study size. As seen in the table, the parameters estimated for the initial 24 subjects had considerable uncertainty for clearance and the volume of distribution. If the study gathers PK samples in half of the patients (N=60), V_1 will be estimated within less than a 40% range (**Table 2**, numbers in red). This should be sufficient to predict the dose of calcium required to reach a target calcium concentration in parturients. Our study will have greater power than predicted by the bootstrap as we will collect 5-6 samples per patient rather than the 2-3 samples obtained in the pilot study.

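### The Table 2 precision correction takes its degrees of freedom from the resampled N and omits a square root, so all six corrected Cl_1 and V_1 ranges are misstated, although the under-40% statement for V_1 at N=60 survives at 23 df

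*Combined protocol and SAP*

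**What the plan says.** The section on pharmacokinetic and pharmacodynamic analysis under Specific Aim 2 supports the precision of the PK estimates with Table 2. The text below the table describes it as "results of 1000 bootstrap replications of data from the original 24 individuals in the pilot PK study". Those same records were also drawn at sizes of 60 and 120, standing for half and all of the planned trial population. For each N the table gives a mean, bootstrap 95% bounds, a range, a correction and a corrected range. The V_1 rows read, with the last figure a percentage:

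- N=24: "V_1 75.6 52.8 88.6 47% 1.76 83"
- N=60: "V_1 75.6 62.9 84.0 28% 1.39 39"
- N=120: "V_1 75.6 68.5 80.6 16% 1.26 20"

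The correction is printed once per N, and the corrected Cl_1 ranges are 173%, 94% and 57%. From the N=60 row the text concludes that "V_1 will be estimated within less than a 40% range" if half the patients give samples, and calls this adequate for predicting the dose that reaches a target concentration. It adds that actual precision should be better than the bootstrap suggests, because 5-6 samples per patient are planned against 2-3 in the pilot. The correction is not defined anywhere. The bootstrap sentence cites reference 18, whose title concerns using a pilot sample to determine sample size. The Figure 1 caption under Preliminary Studies describes "ionized calcium venous blood concentrations from 13 patients who received calcium" and 11 who received placebo, which together make up the 24.

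**The concern.** A factor of the form df/chi-square is a conservative allowance for a variance having been estimated from a limited sample. Here that sample is the 24 pilot patients in every row. Drawing 60 or 120 records with replacement from those 24 narrows the bootstrap interval, as it should, but adds nothing to what is known about between-patient variability. A correction that falls from 1.76 to 1.26 as the resample grows treats simulated patients as pilot data.

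The second difficulty is one of scale. A ratio of variances multiplies an interval width, whereas a width moves with the standard deviation.

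What is at stake is the corrected-range column, which is the only numerical support for the Aim 2 precision statement, and the impression the table gives of how much a larger PK sample buys.

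**Working it through.** **Inputs.** Bounds, means, corrections and corrected ranges come from Table 2. The pilot size of 24 comes from the text below it, and the 13/11 split from the Figure 1 caption. The very small Baseline ranges are set aside.

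**1. Reproduce the range column.** Range = (upper - lower)/mean.

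- Cl_1: (1.70 - 0.78)/0.93 = 98.9%; (1.43 - 0.80)/0.93 = 67.7%; (1.24 - 0.81)/0.93 = 46.2%. Printed: 98, 68, 46%.
- V_1: (88.6 - 52.8)/75.6 = 47.4%; (84.0 - 62.9)/75.6 = 27.9%; (80.6 - 68.5)/75.6 = 16.0%. Printed: 47, 28, 16%.

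**2. Recover the correction.** Try (N-1)/chi-square(0.05, N-1).

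- N=24: 23/13.091 = 1.757 (printed 1.76)
- N=60: 59/42.339 = 1.394 (printed 1.39)
- N=120: 119/94.811 = 1.255 (printed 1.26)

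Lower tails from 0.5% to 25% were tried with df of N, N-1 and N-2, each with and without a square root. Only the 5% tail with N-1 df and no square root matches all three values.

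**3. Reproduce the corrected ranges.** Range x correction gives 173.8, 94.4 and 58.0% for Cl_1 (printed 173, 94, 57%) and 83.2, 38.9 and 20.1% for V_1 (printed 83, 39, 20%). The printed column follows from this rule to within rounding.

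**4. Apply one pilot-based factor on the width scale.** sqrt(23/13.091) = 1.326 in every row.

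| | N=24 | N=60 | N=120 |
|---|---|---|---|
| Cl_1 printed | 173% | 94% | 57% |
| Cl_1 recomputed | 131% | 90% | 61% |
| V_1 printed | 83% | 39% | 20% |
| V_1 recomputed | 63% | 37% | 21% |

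In the N=24 rows the df is already 23, so only the missing square root matters. In the other rows the two errors work in opposite directions. For V_1 at N=60, adding the square root alone gives 27.9% x sqrt(1.394) = 33%, changing the df alone gives 27.9% x 1.757 = 49%, and doing both gives 37%.

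**5. Apparent gain from a larger N.** From N=24 to N=120 the printed V_1 range shrinks by a factor of 83/20 = 4.2, and the recomputed range by 63/21 = 3.0. For Cl_1 the factors are 173/57 = 3.0 and 131/61 = 2.1.

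**6. Sensitivity to the df.** If only the 13 calcium recipients are taken to inform Cl_1 and V_1 (12 df, an assumption), the factor is sqrt(12/5.226) = 1.515. At N=60, V_1 is then 27.9% x 1.515 = 42% and Cl_1 is 67.7% x 1.515 = 103%.

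**The case against.** The strongest reply is that nothing depends on this. The 120-patient sample size comes from the Aim 1 power calculation, 40% is not a prespecified criterion, and with both errors repaired the one cell behind the statement improves from 39% to 37%. All of that stands, and it limits the weight of the point. It does not make the printed column right.

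The purpose of the factor is also inferred. The documents give neither formula nor rationale, and only the title of reference 18 suggests an allowance for a small pilot. That is a fair caution. But three matching factors make coincidence implausible, and if another rationale was intended the sponsor needs to state it.

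The square-root factor is itself an approximation. It is a normal-theory bound for a standard deviation, and the bootstrap intervals are not well behaved: Cl_1 at N=24 runs 0.15 below and 0.77 above its mean. V_1 widths fall as 47.4, 27.9 and 16.0%, where 1/sqrt(N) scaling from the first would give 47.4, 29.9 and 21.2%. The 5% tail is carried over from the table without justification. A 2.5% tail at 23 df gives 39% for V_1 at N=60, and a 10% tail at 12 df gives 38.5%. The recomputed figures are therefore the table's own method applied consistently, not a definitive precision estimate.

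Finally, the 12-df case is arguable. Placebo patients inform the baseline and residual error in a joint mixed-effects fit, and so may inform Cl_1 and V_1 indirectly. No effective df is given. The case is best kept as a sensitivity analysis.

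**Conclusion.** The point holds as a misstated column. All six corrected Cl_1 and V_1 ranges change. Uncertainty is overstated at N=24 (173% against 131%; 83% against 63%) and at N=60 (94% against 90%; 39% against 37%), and understated at N=120 (57% against 61%; 20% against 21%). This rests on the inferred formula, on its reading as an allowance for pilot variability, and on 23 df.

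A reader might infer that the under-40% statement is refuted. The documents do not support that: it holds at 23 df and fails only on the 12-df assumption. The 49% figure is no evidence against it either, because it corrects the df but leaves the scale error in place. Nor should Table 2 be read as the basis for a plan to sample half the patients. Sampling is offered to willing participants, and N=60 is a conditional scenario.

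What can fairly be said is that 39% was reached through two offsetting errors, and that whether the range is below 40% depends on a choice of df, and to a lesser degree of tail, that the plan neither states nor justifies.

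**What to change.** Define the correction in the Table 2 footnote: formula, tail, df and reason for use. Apply one pilot-based square-root factor to all rows, 1.326 at 23 df, or justify a different df. Restate the corrected ranges for N=24/60/120 as 131/90/61% for Cl_1 and 63/37/21% for V_1. In the text, report V_1 at N=60 as about 37%, with about 42% as a sensitivity case if only the 13 calcium recipients are counted.

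Alternatively, support the under-40% statement by simulating the planned 5-6 samples per patient, which would also put a number on the advantage the text claims without quantifying.

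The first route costs one recalculated column and one reworded sentence; the second adds a simulation. Neither changes the sample size or anything in Aim 1.

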Appendix 2: Stanford Labor and Delivery protocol for intrapartum cesarean delivery

Monitoring: All patients undergoing intrapartum cesarean delivery are monitored by continuous pulse oximetry, 3-lead EKG, and noninvasive blood pressure oscillometry. Blood pressures are obtained every 1 minutes prior to fetal delivery. For clinically stable patients at the discretion of the anesthesia team, blood pressure frequency may be decreased to every 2.5-5 minutes after fetal delivery.

Antibiotics:

- Patients without antibiotic allergy or chorioamnionitis receive 2 grams intravenous cefazolin (3 grams if >120 kg) prior to incision and 500 mg of intravenous azithromycin over a one-hour infusion for endometritis prophylaxis.
- Patients with a clinical diagnosis of chorioamnionitis instead receive intravenous ampicillin 2g, gentamycin 5 mg/kg over a one-hour infusion, and clindamycin 900 mg intravenously

Neuraxial anesthesia:

- Patients with a labor epidural in situ receive epidural top-up with divided doses of 2% lidocaine with epinephrine 1:200,000 to achieve a T4 dermatomal level to pinprick bilaterally (generally 15-25 mL total volume). 100 mcg epidural fentanyl is added at the discretion of the attending anesthesiologist. All patients receive 3 mg epidural morphine prior to case conclusion for postoperative analgesia.
- Patients without a labor epidural in situ receive a single-shot spinal or combined spinal-epidural anesthetic, with a standard intrathecal medication cocktail of 1.6 mL 0.75% hyperbaric bupivacaine, 15 mcg fentanyl, and 100 mcg morphine.

Uterine tone assessment and uterotonic medications:

- At the time of fetal delivery, 2 units of intravenous oxytocin are administered, and an oxytocin infusion is initiated at 7.5 units/hr
- 2 minutes after fetal delivery, the uterine tone is assessed by palpation of the uterine fundus and rated on a scale from 0-10, with 0 representing a completely atonic uterus and 10 representing a firm and completely contracted uterus. This score is recorded. For uterine tone score <8/10, an additional 2 units oxytocin are administered, and oxytocin infusion increases to 15 units per hour
- 7 minutes after fetal delivery, uterine tone is again assessed by palpation and score recorded. For scores <8/10, oxytocin 2 units are administered for a 3rd time, oxytocin infusion increases to 30 units/hr, and the anesthesia and obstetric teams discuss whether a second line uterotonic may be warranted. If so, the anesthesia team begins preparation of the second line uterotonic agent. This agent is administered if uterine tone is still deemed inadequate at the discretion of the anesthesia and obstetric teams.
- 12 minutes after delivery, uterine tone is again assessed by palpation and score recorded. For scores <8/10, the obstetric and anesthesia teams will discuss whether a second line uterotonic may be clinically indicated.
- The uterotonic protocol outlined can be changed based on clinical picture or obstetrician request.

Quantitative blood loss:

Quantitative blood loss (QBL) is measured for all cesarean deliveries by a standardized protocol. The protocol follows nationally recommended methodology that combines gravimetric (measurement of suction cannister contents after subtraction of the amniotic fluid volume) and volumetric (weighing all surgical sponge and drape and subtracting dry weights) QBL.^{1,2} This process is performed by the clinical labor and delivery nurses, all of whom receive standardized training in performing the technique.

1. Quantitative Blood Loss in Obstetric Hemorrhage: ACOG COMMITTEE OPINION, Number 794. *Obstetrics and gynecology* 2019;134(6):e150-e156.

Appendix 3 Protocol Sheet: CALCIUM CHLORIDE FOR PREVENTION AND TREATMENT OF BLOOD LOSS FROM UTERINE ATONY DURING INTRAPARTUM CESAREAN DELIVERY

STUDY ID NUMBER (on study drug syringe): _____

Reminder: This study investigates whether one gram of calcium chloride IV, administered over 10 minutes starting 2 minutes after fetal delivery, decreases blood loss from uterine atony during intrapartum cesarean.

- Primary outcome: Quantitative Blood Loss
- Secondary outcomes: Uterine tone scores, uterotronics, side effects

Please confirm inclusions with a checkmark or X:

- Patient is 18-55 years old
- Patient is having an intrapartum cesarean delivery
- Patient received oxytocin infusion for labor induction or augmentation.
- Patient still wants to participate and has signed consents

Please confirm this patient has NO EXCLUSIONS:

- Patient does not have renal dysfunction with serum Cr>1.0 mg/dL
- Patient does not have any known cardiac conditions
- Patient is not receiving a calcium channel blocker (none in last 24 hours)
- Patient is not receiving digoxin for a maternal or fetal indication
- This is not an emergency in which participation in the study could hinder or delay care

Study drug:

- The syringe contains **60mL saline with 1-gram Calcium Chloride OR 60mL saline placebo**
- Administer via syringe pump and microbore tubing over 10 minutes
 - Program a basic infusion on Alaris pump for basic infusion, **360mL/hr**
 - Attach microbore tubing to injection port closest to the patient
 - Start infusion **2 minutes after fetal delivery** (1 minute after cord clamp)
- Assume that every infusion contains 1 gram of calcium and **discontinue** if concerns for extravasation (arm pain and redness or signs of infiltration), hemodynamic compromise (bradycardia and hypotension most common). Contact [name] via email or cell [contact] for any concerns and document on next page.

PLEASE FILL OUT ALL INFORMATION ON THE NEXT PAGE.

STUDY ID NUMBER (on study drug syringe): _____

USE EPIC COMPUTER CLOCK FOR ALL TIMES

Fetal Delivery and oxytocin 2 unit bolus :

Time: _____

2 minutes after fetal delivery:

• Ask obstetrician to rate uterine tone 0-10: Tone: _____

• Start study drug infusion: Time Started: _____

• *If infusion was paused or stopped* Time paused: _____

Time restarted: _____

7 minutes after fetal delivery:

• Ask obstetrician to rate uterine tone 0-10: Tone: _____

12 minutes after fetal delivery:

• Ask obstetrician to rate uterine tone 0-10: Tone: _____

19 minutes after fetal delivery:

• Ask obstetrician to rate uterine tone 0-10: Tone: _____

Side effects (did the patient experience any of the following possibly related to the study drug? Circle Yes/No)

- Arm or IV site discomfort? YES / NO
- Concern for extravasation? YES / NO
- Heart rate change or arrhythmia? YES / NO Describe: _____
- Hypertension or hypotension YES / NO Describe: _____
- Flushing YES / NO
- Abnormal sensations or tastes YES / NO Describe: _____
- Nausea YES / NO
- Vomiting YES / NO
- Other YES / NO Describe: _____

Was the infusion started exactly 2 minutes after fetal delivery? YES / NO

If not, please explain why: _____

Was the whole infusion given? If not or if paused, please explain why below

STUDY ID NUMBER (on study drug syringe): _____

If patient consents to up to 6 lab draws of 0.5mL venous blood:

- Research staff (fellow or research assistant) to analyze samples in a **different operating room**.
- **DO NOT** participate in patient care or converse with staff or the patient in the delivery room other than to obtain permission to obtain blood samples, as your knowledge of these lab values could compromise blinding of the patient, anesthesiologist, or obstetrician.

Times to target for blood samples relative to the start of study drug infusion:

• Baseline (prior to study drug start)	• 10-30 minutes
• 0-5 minutes	• 30-60 minutes
• 5-10 minutes	• 60-240 minutes

Carefully document the time that the blood was drawn using **EPIC computer clock** for each sample.

Use the **research iSTAT machine** and research EG7+ cartridges.

For patient ID on the iSTAT, please enter the study ID number and not the MRN

Time study drug started: _____

Baseline: Time: _____ pH: _____

iCa: _____

Sample 2: Time: _____ pH: _____

iCa: _____

Sample 3: Time: _____ pH: _____

iCa: _____

Sample 4: Time: _____ pH: _____

iCa: _____

Sample 5: Time: _____ pH: _____

iCa: _____

Sample 6: Time: _____ pH: _____

iCa: _____

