Patient safety: All potential side effects of calcium will be recorded as part of this study, including flushing, arm discomfort, nausea, vomiting, bradycardia, tachycardia, arrhythmia, and hypertension. A single dose of dilute CaCl_2 , infused slowly through an intravenous (IV) line in the sensate upper extremity of an un-sedated patient, is unlikely to cause severe adverse effects. The major concern with CaCl_2 is tissue necrosis from extravasation. Any discomfort in the IV site will warrant immediate study drug infusion discontinuation with careful assessment of the extremity. The clinical anesthesiologist caring for the patient will also monitor for potential hemodynamic consequences of calcium infusion including bradycardia, hypotension, or hypertension. The anesthesiologist providing care to the patient will be instructed to assume the study drug contains 1 gram of CaCl_2 for all cases, and to immediately discontinue the infusion if they believe any the patient may be having a severe adverse effect. A data safety monitoring committee of two attending anesthesiologists with no involvement in the trial and with a track record of data safety monitoring has been created for this trial. Any potential adverse events including patient hemodynamic compromise or concern for drug extravasation will be reviewed immediately ad hoc, and they will determine whether unblinding is required and when the study may resume.

Management of hypercalcemia: Acute hypercalcemia may manifest as altered mental status, bradycardia, or hypotension. We do not anticipate clinical hypercalcemia given the patient population (young, healthy, renal dysfunction and digoxin use are contraindications), the dilute and slow infusion, the single dose of calcium, and the excellent patient tolerance and peak ionized calcium levels obtained during our pilot study. However, management of acute hypercalcemia would include immediately pausing the infusion if still running, administering a fluid bolus of 500mL to 1000mL isotonic fluid, and obtaining a serum calcium level at the discretion of the clinical anesthesia team. If necessary, the team could consider additional administration of 10-20mg intravenous furosemide to lower serum calcium further if needed.

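### The side-effect form merges opposite hemodynamic events into two unthresholded yes/no items limited to events thought possibly drug-related, which weakens the safety comparison under Aim 1

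*Combined protocol and SAP*

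**What the plan says.** The Patient safety section promises wide recording: "All potential side effects of calcium will be recorded as part of this study". Its list of events runs "including flushing, arm discomfort, nausea, vomiting, bradycardia, tachycardia, arrhythmia, and hypertension". Hypotension is not in that list. The same section does name hypotension, with bradycardia and hypertension, among the hemodynamic consequences that the anesthesiologist is to monitor. The study drug instructions in the Appendix 3 Protocol Sheet describe bradycardia and hypotension as the most common hemodynamic compromise.

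The form that collects these events, under Side effects in Appendix 3, has two hemodynamic items: "Heart rate change or arrhythmia? YES / NO Describe" and "Hypertension or hypotension YES / NO Describe". Both sit under the question "did the patient experience any of the following possibly related to the study drug? Circle Yes/No". Neither item has a numeric criterion, and the form has no field for a heart rate or blood pressure reading.

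Appendix 3 lists side effects among the secondary outcomes. The only analysis text that applies is the general rule under Data Analysis: proportions, compared by chi-square or Fisher's exact test, two-sided at 0.05. It does not say whether the ticked answer or the described direction is analysed.

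Appendix 2 (Monitoring) states that every patient has continuous pulse oximetry, 3-lead EKG and noninvasive blood pressure. After delivery, blood pressure may be taken every 2.5 to 5 minutes in stable patients. No extraction or analysis of these readings is planned.

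**The concern.** A patient with high pressure and a patient with low pressure both score YES on the same item, and so do a patient with bradycardia and one with tachycardia. The general rule for categorical data most naturally takes the YES/NO answer as its input. Background events in one direction then add noise to any calcium effect in the other, and shifts in opposite directions subtract from each other.

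The relatedness wording acts earlier, at recording. All patients receive neuraxial anesthesia and oxytocin. An event that the clinician puts down to either of these can be circled NO, and an event circled NO need not be described anywhere on the form.

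Both features make it easier to find no difference between arms. For a trial that hopes to report no safety concern, loss of power favours the reassuring answer.

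**Working it through.** The plan states no safety power and no hemodynamic event rates. The pilot reports only that there were no adverse hemodynamic consequences. There is therefore no stated figure to reproduce, and every event rate below is an assumption.

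**Inputs from the plan.** n = 60 per arm (Sample size), 1:1 allocation (Subject exposures), two-sided alpha 0.05 (Data Analysis).

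**Formula.** Power = Φ[(|p1 − p2| − 1.96·SE0)/SE1], with SE0 = √(2p̄(1 − p̄)/n) and SE1 = √([p1(1 − p1) + p2(1 − p2)]/n). Hypertension and hypotension are taken not to occur in the same patient, so the merged rate is their sum.

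**1. Effect in one direction.** Hypertension 5% on placebo and 20% on calcium; hypotension 30% in both arms.

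- Hypertension alone, 5% vs 20%: p̄ = 0.125, SE0 = 0.0604, SE1 = 0.0588. (0.15 − 0.1183)/0.0588 = 0.54, so power is 0.705.
- Merged item, 35% vs 50%: p̄ = 0.425, SE0 = 0.0903, SE1 = 0.0892. (0.15 − 0.1769)/0.0892 = −0.30, so power is 0.382.

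The difference is 15 points in both cases. The background of hypotension raises the variance and cuts power from about 70% to about 38%. This is dilution.

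**2. Effects in opposite directions** (placebo to calcium).

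| Hypotension | Hypertension | Merged | Power, hypotension | Power, hypertension | Power, merged |
|---|---|---|---|---|---|
| 30% to 20% | 5% to 15% | 35% vs 35% | 24% | 45% | 5% |
| 30% to 15% | 5% to 20% | 35% vs 35% | 50% | 70% | 5% |
| 30% to 10% | 5% to 25% | 35% vs 35% | 79% | 88% | 5% |
| 30% to 15% | 5% to 10% | 35% vs 25% | 50% | 18% | 22% |

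Offsetting is complete only when the fall equals the rise, and partial otherwise (last row). As a count example, hypertension in 12/60 vs 3/60 gives Fisher p = 0.025. With hypotension 3/60 vs 12/60, the merged item reads 15/60 in each arm.

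**3. Relatedness filter.** Suppose blinded clinicians tick the same fraction c of events in each arm, and true rates are 10% vs 30%.

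| c | Rates ticked | Risk ratio | Risk difference | Power |
|---|---|---|---|---|
| 100% | 10% vs 30% | 3.0 | 20 points | 79% |
| 75% | 7.5% vs 22.5% | 3.0 | 15 points | 64% |
| 50% | 5% vs 15% | 3.0 | 10 points | 45% |
| 25% | 2.5% vs 7.5% | 3.0 | 5 points | 24% |

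The ratio is unchanged, so the filter cancels nothing. It shrinks the absolute difference and the power.

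The losses in steps 1 and 3 should not be added together. A filter that removed most background hypotension would also leave less of it in the merged item to dilute the comparison.

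**The case against.** The strongest reply is that direction is captured. Both hemodynamic items carry a Describe line, which flushing, nausea and vomiting lack, and staff are told to complete all information on that page. The Patient safety section lists the events separately, which points towards reporting by type. This stands in part. It would be wrong to infer that bradycardia can never be told from tachycardia, or that a calcium effect will cancel out. But no rule says that the text will be coded, there is no common threshold, and the line does not recover events circled NO.

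A reader might also infer cancellation from the form alone. The documents do not support that. It needs an analysis of the tick alone, which they neither state nor exclude, and calcium lowering one event about as much as it raises the opposite one. They name hypotension as a possible consequence of calcium and nowhere suggest that calcium reduces it. Smaller shifts could be missed even with separate boxes: 10/60 vs 3/60 gives Fisher p = 0.075, and 9/60 vs 3/60 gives p = 0.13.

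Nor is the relatedness wording a clear contradiction. All potential side effects of calcium and events possibly related to study drug can be read as the same scope. Raters are blinded, and the anesthesiologist is told to assume that every infusion contains calcium, so differential filtering is not shown. A filter that removed mainly unrelated events could even sharpen the comparison; the power loss above assumes equal capture of all events.

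Finally, patients are protected in other ways: infusion pauses are documented with reasons, and possible adverse events go to immediate ad hoc review by the safety committee. That stands, but it concerns individual cases, not the comparison between arms.

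**Conclusion.** The point holds as a weakness in how a secondary safety outcome is measured. The form is coarser than the event list in the Patient safety section, sets no criterion, leaves direction to free text with no coding rule, and restricts recording by perceived relatedness. The recording list also omits hypotension, which the monitoring text and the form both name.

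If the items are compared as ticked, the supported consequence is dilution: about 38% power against 70% in the one-direction example. Offsetting is possible but not shown to be likely. The filter lowers counts, and under equal capture it lowers power (79% to 45% when half of events are ticked, at 10% vs 30%).

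These sizes rest on assumed rates, on the two blood pressure events being mutually exclusive, and on analysis of the YES/NO answer. The primary outcome and bedside monitoring are not affected. As captured, the form gives weak support to the safety part of the Aim 1 hypothesis. The change is cheap and worth making.

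**What to change.** - Replace the two hemodynamic items in Appendix 3 with five: bradycardia, tachycardia, arrhythmia, hypertension and hypotension.
- Ask about occurrence from study drug start to the end of surgery regardless of cause, with relatedness as a separate question. Both the unfiltered and the filtered comparison can then be reported.
- Add hypotension to the recording list in the Patient safety section.
- State a safety analysis that compares each event by arm. Use measurement definitions that the investigators set before unblinding, applied to the heart rate and post-delivery blood pressure readings already taken under Appendix 2. The one-minute blood pressure interval there applies before delivery and so before study drug; afterwards, 2.5 to 5 minutes is allowed in stable patients, and the definitions should allow for that spacing.
- For patients already enrolled, code the Describe text by direction while still blinded.

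The cost is a form revision and a data pull, assuming that the monitor readings are kept in the anesthesia record. The downside is higher raw event rates in both arms, because effects of the neuraxial block and oxytocin will be counted. The separate relatedness question lets the reader see past that. No treatment or monitoring changes.
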